Patient Population	Newborn infants $\geq$ 36 weeks gestation which satisfy all St Michael's Hospital standard inclusion criteria for cooling (i.e. at risk of brain injury following poor condition at birth) and which additionally satisfy the inclusion criteria of this investigation for the administration of xenon by inhalation. Cooling should be started within 3h of age and xenon within 5. Use of a shorter treatment delay in these entry criteria will optimize the possibility of finding an effect if there is one.
Population Size	16 babies in each of 2 groups
Structure	Single centre prospective randomised clinical pilot study
Duration of Participation	Xenon administration period of 18 hours. Recruitment period up to 18 months from start of study. Short and long term monitoring until 18 months of age. Therefore total study duration 3 years.
Method of Assignment	Comparative study. Neonates meeting all entry criteria can be included.
Randomisation	Patients will be randomised between cooling (standard treatment) and xenon+cooling groups as this is a comparative study. Patients will be randomised on a 1:1 basis to receive either conventional cooling therapy or cooling plus xenon therapy.

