Statistical Analysis	
This is a randomised pilot study. Data presentation will include descriptive statistics only. These will be compared in the 2 treatment groups but also to recordings of the same variables in a similar group of 45 infants (recruited to cooling only from the same entry criteria) recently treated in our department (historical control data). Differences between the groups will be estimated.
 
Sample size is 16 infants in each group. In accordance with the paper by Julious (Appendix 11), 12 is a large enough number to estimate the mean value of short term outcome variables for the group. The study does of course not have the power to test outcome. The main purpose of this randomised pilot study is to examine whether early recruitment is feasible, secondly whether the short term biological markers show the expected range of values in the cooled only group as compared to our historical controls. Our advisory statistician for this study is [name] who also advised all our experimental xenon work as well as the recent clinical feasibility study.
 
By April 2013 we have recruited 8 babies to standard cooling therapy and 7 babies to xenon plus cooling; we have failed to recruit approximately the same number due to failure to commence xenon delivery at St Michael's Hospital within 5 hours of birth. This is due to the time it takes to retrieve infants from the regional hospitals. Since April 2013, our xenon delivery system has been transportable and we have so far successfully started xenon treatment on two babies in the

Reference:	CH
Issue:	2
Revision:	3
Issue Date:	1 May 2013
Page	6 of 49

	local hospital and transferred them to St Michael's Hospital while xenon was being delivered en route. This ability to commence xenon at the referring trust enabled us to recruit consecutive infants that would otherwise have been missed. We wish to assess the feasibility of recruiting now we have xenon in the ambulance by increasing the number of babies by 8.
Adverse Events	Volunteered and Elicited

Reference:	CH
Issue:	2
Revision:	3
Issue Date:	1 May 2013
Page	7 of 49

SECTION	CONTENTS	PAGE
	Confidentiality Statement	2
	Protocol Summary	3
	Overview	9
1.0	Background and Introduction	9
1.1	Background	9
1.2	Review of Literature	9
1.3	Rationale for the Study	10
2.0	Objectives	11
2.1	Primary Endpoint	11
2.2	Secondary Endpoint	12
3.0	Study Design	13

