#### **Group size calculation**

Sixteen babies will be recruited into each group (cooling+xenon vs cooling alone) at random. The cooling will be applied as standard treatment if cooling criteria are met. Addition of xenon in combination with this underlying cooling will take place in the group randomised to receive cooling + xenon.

For pilot studies of this type the recommendation is a sample size of 12 per group. The justifications for this sample size are based on

- i) Feasibility – allows convenient block sizes, for example our intention for a data review committee to review data sets at block intervals of 4 neonates.
- ii) Precision about the mean – little additional precision to be gained by having a larger group size than 12 [44].
- iii) Precision about the variance – little additional precision to be gained by having a larger group size than 12 [44].

Reference [44] presented in full in Appendix 10.

The first 15 neonates were recruited in a period where the xenon ambulance transfer system was not ready for use. The clinical staff employed to recruit and deliver the xenon in the ambulance needed time to gain experience using the system before using it independently away from the base hospital without the supervision of [name]. This has led to a similar number of babies which we failed to recruit (due to the time limitation) as the number recruited to

Reference:	CH
Issue:	2
Revision:	3
Issue Date:	1 May 2013
Page	25 of 49

xenon. We therefore wish to recruit a further 8 babies to assess the feasibility to recruit, more reliably, consecutive babies fulfilling the entry criteria within the confines of the protocol

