## 8.0 Assessment of Safety

### 8.1 Data Review Group.

An external Data monitoring Group will be set up and appropriately constituted with clearly defined terms of reference. Their role will be to independently review the safety of the study after every 4th xenon patient has been recruited i.e.

every 4 xenon babies and in the light of this make appropriate recommendations to the study team.

The group will meet when every 4 xenon-treated babies have been enrolled. The Data Monitoring Group will also meet in the event of a death, regardless of cause. This meeting will take place within ~14 days of the death and recruitment into the study will continue in the meantime. This meeting could be in person or take the form of a teleconference.

N.B. In our previous neonatal feasibility/safety study of xenon+cooling a partial external committee met at intervals of every other baby enrolled. One outcome of this study was that the xenon gas itself did not cause any significant physiological or biochemical changes or other problems and neither did the use of a breathing system functionally the same as the one to be used in this study. This explains our choice of a 4 enrolled xenon baby interval for the xenon+cooling group in this study.

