#### Stopping rule:

Mortality since cooling became standard of care at St Michaels hospital (inborn and outborn) fell from 34% to 25%. With this (25%) underlying mortality it is not unlikely, for example, that the two first infants might die ( $p=0.06$ ). If the study is allowed to continue and also the third infant in the xenon group dies, the probability that this is a random event is very small ( $p=0.016$ ) and recruitment should be stopped and the protocol reviewed.

From then on (n is the number of 'xenon' babies included in the study):

n deaths

- 3 3 of 3 stop
- 4 3 of 4 stop
- 5 4 of 5 stop
- 6 4 of 6 stop
- 7 4 of 7 stop
- 8 5 of 8 stop
- 9 5 of 9 stop
- 10 5 of 10 stop
- 11 5 of 11 stop
- 12 6 of 12 stop

If a few more than 12 infants were to be included in the xenon arm of this study the number of deaths used as the stopping number should be 40% of the total number.

This stopping rule is based on two considerations:

1. Probabilities given 25 % mortality without Xe
2. Stricter rule with more babies included

(See Appendix A6)

Reference:	CH
Issue:	2
Revision:	3
Issue Date:	1 May 2013
Page	40 of 49

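### Does the mortality stopping rule become unusable for xenon infants 13 to 16, where only a 40% sentence applies?

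*Protocol*

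**What the plan says.** The Stopping rule in section 8.3 lists boundaries for 3 to 12 xenon infants: 3 deaths at 3 and 4 infants, 4 at 5 to 7, 5 at 8 to 11, and 6 at 12. It defines the row index: "n is the number of 'xenon' babies included in the study". Beyond the table it continues: "If a few more than 12 infants were to be included in the xenon arm of this study", then "the number of deaths used as the stopping number should be 40% of the total number". It gives two considerations behind the rule, the 25% mortality expected without xenon and "Stricter rule with more babies included", and refers to Appendix A6, the study statistician's letter, which is not in the supplied text.

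The planned size is larger than the table. The Protocol Summary gives "16 babies in each of 2 groups", and the group size paragraph of section 3.3 states "Sixteen babies will be recruited into each group (cooling+xenon vs cooling alone) at random". The Summary explains the change: "We wish to assess the feasibility of recruiting now we have xenon in the ambulance by increasing the number of babies by 8". Sixteen per arm is 32; less 8 is 24, or 12 per arm, which is where the table stops.

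Section 8.1 has the external group review after every fourth xenon infant and adds: "The Data Monitoring Group will also meet in the event of a death, regardless of cause".

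**The concern.** The table was evidently built for 12 xenon infants. When the arm grew to 16, the last quarter of it was left to a sentence that still treats those infants as a contingency. Forty per cent of 13, 14 and 16 is not a whole number, and the sentence does not say how to round, or whether the total means xenon infants so far or the planned 16. Different combinations give different boundaries. Six deaths among 13, 14 or 15 infants could mean stop on one combination and continue on another; five deaths among 13 or 14, and six among 16, also depend on the reading.

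This is the pre-set numerical trigger for halting recruitment of newborns because of deaths. If its value is open, the external group would have to choose the boundary after seeing the deaths, which is what a pre-set rule is meant to avoid. Recruitment also continues during the roughly 14 days before that group meets.

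**Working it through.** **Inputs.** Mortality without xenon 25%, the table for 3 to 12 infants, and the 40% sentence (all section 8.3); planned xenon arm 16 (section 3.3).

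**The protocol's own figures.** First two infants die: 0.25² = 0.0625 (stated 0.06). First three: 0.25³ = 0.0156 (stated 0.016). Both reproduce.

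**The 40% products.** 0.4 × 13 = 5.2; 0.4 × 14 = 5.6; 0.4 × 15 = 6.0; 0.4 × 16 = 6.4.

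**Possible readings.** The chance of stopping by infant 16 comes from an exact infant-by-infant recursion through the table and then each extension, taking each outcome as known before the next infant is counted. The 40% mortality column is an assumption, not a protocol figure.

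| Reading | Deaths to stop at 13/14/15/16 | Chance at 25% | Chance at assumed 40% |
|---|---|---|---|
| Running count, deaths reach 40% (round up) | 6/6/6/7 | 19.9% | 64.6% |
| Running count, nearest | 5/6/6/6 | 26.1% | 73.0% |
| Running count, round down | 5/5/6/6 | 28.8% | 75.5% |
| Planned 16, down or nearest | 6/6/6/6 | 23.1% | 70.4% |
| Planned 16, round up | 7/7/7/7 | 16.7% | 58.8% |

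The table to n = 12 contributes 14.75 points of every figure in the 25% column.

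**First row by hand.** At 25% mortality the chances of being unstopped at n = 12 with 5, 4 and 3 deaths are 0.0364, 0.1721 and 0.2534.

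- Sixth death at 13: 0.0364 × 0.25 = 0.0091.
- Five deaths, unstopped at 13: 0.0364 × 0.75 + 0.1721 × 0.25 = 0.0703. Sixth death at 14: 0.0703 × 0.25 = 0.0176.
- Four deaths at 13: 0.1721 × 0.75 + 0.2534 × 0.25 = 0.1924. Five, unstopped at 14: 0.0703 × 0.75 + 0.1924 × 0.25 = 0.1008. Sixth death at 15: 0.1008 × 0.25 = 0.0252.
- At 16 a seventh death is needed, but an unstopped path has at most five deaths at 15, so 0.

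These sum to 0.0519, and with 0.1475 give 0.199.

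**Which readings fit the text.**

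1. *Six deaths at 13 to 15.* On the running count, 6 is at least 5.2, 5.6 and 6.0, so the answer is stop under any rounding. It is also stop if the total is 16 and 6.4 goes to 6. Only the planned 16 combined with rounding up gives continue.
2. *That one combination* asks for 7 of 13, or 53.8%, above the 50.0% at 6 of 12. Where the printed boundary steps up, the shares fall each time: 3/3 = 100%, 4/5 = 80%, 5/8 = 62.5%, 6/12 = 50%. A rise to 53.8% would be the first, against the stated aim that the rule tighten. On 6/6/6/7 the next step is 7/16 = 43.8%, which continues the fall. The rise from 5/11 = 45.5% to 6/12 = 50.0% is the ordinary saw-tooth of whole numbers, also seen from 3/4 = 75% to 4/5 = 80%.
3. *Rounding down or to nearest on the running count* lowers the boundary from 6 at 12 to 5 at 13. The table lets 5 of 12 (41.7%) continue, so recruitment would then stop because the thirteenth infant survived. That path has probability 0.0364 × 0.75 = 0.0273 at 25% mortality. No reader would intend this.
4. *The word total.* The sentence speaks of infants included in the xenon arm, and the table defines n as xenon infants included. The running count is the plain reading.

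**The case for a change.** The strongest argument for a change is that a safety boundary should not need interpretation. Appendix A6 is not available, 40% of 12 is 4.8 while the table prints 6, so the printed rows show no rounding convention, and across the five readings the chance of stopping at 25% mortality runs from 16.7% to 28.8%. Between 6/6/6/7 and 7 throughout there is a 5.2% chance of a review at 13 to 15 with opposite answers, and a 3.3% chance (0.1993 − 0.1667 = 0.0326) that they still differ at 16. At an assumed 40% mortality the first of these is 13.8%. With only 7 xenon infants recruited by April 2013, the last four still lay ahead, and four extra table rows would be cheap.

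The arithmetic stands, and so does the remark that the sentence was not updated when the arm grew. The conclusion does not follow. The wide range comes from readings that lower a boundary as infants accrue or loosen a rule described as tightening. A whole count compared with a percentage needs no rounding rule: either deaths have reached 40% or they have not. A difference at n = 16 matters little, because the xenon arm is then full. Asking for printed rows would record the rule already implied; it would not supply a better one.

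**Conclusion.** No change is needed. Section 8.3 does cover infants 13 to 16, and its natural reading gives 6, 6, 6 and 7 deaths, in line with the printed table and the stated intent. What is left is a clerical lag: a contingency clause kept after 16 became the plan. On the natural reading the chance of stopping by infant 16 at 25% mortality is 19.9%, of which 5.2 points arise after infant 12. The real looseness is at five deaths with 13 or 14 infants and six with 16, and there the alternatives require a boundary that falls from 6 to 5 or a total other than the running count. Deaths cannot pass unnoticed, because the external group convenes after each one.

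This rests on two assumptions. First, each outcome is known before the next infant is counted; recruitment during the wait for a meeting could make n at review larger than n at the death, and this is not modelled. Second, Appendix A6, which could not be seen, does not contradict the running-count reading. No threshold is endorsed here beyond describing what the text implies.

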#### 8.4 Adverse Events (AEs)

Adverse events will be recorded in accordance with UH Bristol's Research Related Adverse Event Reporting Policy.

#### 8.5 AE Definitions

Adverse event

"Any untoward medical occurrence in a patient or clinical trial subject administered a medicinal product and which does not necessarily have a causal relationship with this treatment"

Adverse reactions

"All untoward and unintended responses to an investigational product related to any dose administered"

Serious adverse event

"Any untoward medical occurrence or effect that at any dose results in death, is life – threatening, requires hospitalisation or prolongation of existing hospitalisation, results in persistent or significant disability or incapacity or is a congenital anomaly or birth defect."

Unexpected adverse reaction

"An adverse reaction, the nature or severity of which is not consistent with the applicable product information (e.g. investigator's brochure for an unauthorised medicinal product or summary of product characteristics for an authorised product)"

#### Assessment of causality

1. **Not related** – temporal relationship of the onset of the event, relative to the administration of the product, is not reasonable or another cause can by itself explain the occurrence of the event.
2. **Unlikely**
3. **Possibly related** – temporal relationship of the onset of the event, relative to administration of the product, is reasonable but the event could have been due to another, equally likely cause.
4. **Probably related** – temporal relationship of the onset of the event, relative to the administration of the product, is reasonable and the event is more likely explained by the product than by another cause.
5. **Definitely related** – temporal relationship of the onset of the event, relative to the administration of the product, is reasonable and there is no other cause to explain the event or a re challenge (if feasible) is positive.

Of the above definitions,

"possibly", "probably" and "definitely" related to an investigational medical product are considered adverse reactions "unlikely" and "not related" do not qualify as a causal relationship.

The severity and causality of a serious adverse event, adverse event or SUSAR (Suspected Unexpected Serious Adverse Reaction) should be assessed by a qualified medical practitioner, usually (but not always) the Chief Investigator (CI).

Adverse events or reactions that are not life threatening and do not result in death or hospitalisation may also be considered serious if they jeopardise the subject or require intervention.

All adverse events must be reported to the sponsor immediately, unless they are identified as not requiring this in the trial protocol.

It is then the responsibility of the sponsor to report the incident to the MHRA

Clinical Study Protocol  Neonatal Xenon Breathing Study (CoolXenon2 Study)	Reference:	CH
	Issue:	2
	Revision:	3
	Issue Date:	1 May 2013
	Page	41 of 49

## 8.6 AE Classification

The Investigator(s) will establish the causality of AEs.

## 8.7 AE Recording

All Adverse Events volunteered by study Patients or elicited by the Investigator must be recorded on the AE forms provided. All AEs must be recorded whether or not considered drug / treatment related.

## 8.8 AE Reporting

The Investigator must report by telephone all serious AEs to the Sponsor immediately upon discovery, and forward the completed AE form as soon as it is available. If the event has been classified serious / severe, or there is any suspicion that the AE was caused by a test article, details of medical history, concomitant medication and an assessment of compliance with therapy should accompany the AE form. The Investigator must also report the resolution reported AEs promptly.

Non-serious AEs should be reported at the next routine contact.

The time period allowed for reporting such events to the MHRA are as follows:

Reaction which is fatal or life threatening, as soon as possible but no later than 7 days after first occurrence

Reaction which results in hospitalisation /disability/congenital anomaly, as soon as possible, but no later than 15 days after first occurrence

## 8.9 Reporting Responsibilities to Regulatory Authorities, Investigators and Ethics Committees

The study will be performed subject to Research Ethics Committee (REC) approval, including any provisions of Site Specific Assessment (SSA), and local Research and Development (R&D) approval. The Sponsor will send appropriate safety notifications to regulatory authorities in accordance with applicable laws and regulations.

The Investigator must comply with any applicable site-specific requirements related to the reporting of SAEs involving his/her subjects to the Ethics Committee that approved the trial.

In accordance with ICH GCP guidelines, the Sponsor will inform the Investigator of "findings that could adversely affect the safety of subjects, impact the conduct of the trial or alter the Ethics Committee approval to continue the trial".

## 9.0 Data Analysis and Statistical Plan

### 9.1 Statistical Analysis

This is a randomised pilot study. Data presentation will include descriptive statistics only. These will be compared in the 2 treatment groups but also to recordings of the same variables in a similar group of 45 infants (recruited to cooling only from the same entry criteria) recently treated in our department (historical control data). Differences between the groups will be estimated

Sample size is 16 infants in each group. In accordance with the paper by Julius (Appendix 11), 12 is a large enough number to estimate the mean value of short term outcome variables for the group. The study does of course not have the power to test outcome. The main purpose of this randomised pilot study is to examine whether early recruitment is feasible, secondly whether the short term biological markers show the expected range of values in the cooled only group as compared to our historical controls. Our advisory statistician for this study is [name] who also advised all our experimental xenon work as well as the recent clinical feasibility study.

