#### **Early predictors of outcome**

#### **For the main analysis we will use**

Time to recovery after birth of a normal aEEG [1]

MRI scan before 14 days of life [33, 2]

Peak LDH value within 72h of life [4, 34]

We will also collect data on:

Plasma glucose at birth (in cord blood)

Age in hours after birth when plasma lactate has fallen to 5mmol/L

Different inotropic drugs needed and the total duration in hours of any inotropic support

Number of anticonvulsants given

Amount and duration of sedation (e.g.morphine)

Age at full oral feeds (breast or bottle or tube)

Neonatal hearing screening result before 14 days of life

Clinical examination at birth, at 7 days of age and at discharge including weight and head circumference

Neurodevelopmental follow up is a part of the routine follow up of infants with HIE, Bayley examination at 18 months of age.

Disability will be defined as any of:

Bayley II mental developmental scale (MDI) score less than 70.

Bayley II motor development scale (PDI) score less than 70. MDI and PDI will also be calculated as DQ, developmental score as this allows a larger range of score for those functioning at a low level [35]. Bilateral cortical visual impairments Hearing loss needing amplification > 40 DB.

In addition any Adverse Events will be recorded and criteria have been devised for stopping the study early if necessary. This includes a Data Review Panel to review data when 4 xenon infants have undergone xenon treatment.

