#### **St Michael's hospital standard inclusion criteria for cooling**

Standard Hypothermia Treatment Criteria for 72 hrs of cooling — all of criteria A, B, and C.

A Infants > 36.0 weeks gestation (clinical assessment) with at least ONE of the following:

- 1 Apgar score <5 at ten (10) minutes after birth

Reference:	CH
Issue:	2
Revision:	3
Issue Date:	1 May 2013
Page	32 of 49

2      Continued need for resuscitation, including endotracheal or mask ventilation, at ten minutes after birth

3      Acidosis defined as either umbilical cord pH or any arterial, venous or capillary pH within 60 minutes of birth less than pH 7.00

4      Base deficit greater than or equal to 16 mmol/L in umbilical cord blood sample or any blood sample within 60 minutes of birth (arterial or venous blood). If the infant meets criterion A then assess for neurological abnormality using criterion B and C (by trained personnel):

B      Moderate or Severe encephalopathy as evidenced by any of the following --

1      Altered state of consciousness (reduced or absent responses or pathological irritability and hyper responsive and at least ONE or more of the following:

2      Hypotonia

3      Abnormal reflexes including oculomotor or pupillary abnormalities

4      Absent or weak suck

5      Clinical seizures, as recorded by trained personnel

*And*

C      At least 30 minutes duration of amplitude-integrated electroencephalography (aEEG) recording that shows abnormal background aEEG activity. The decision to cool is based on the worst section of the aEEG, not the best (al Naqeeb, et al, 1999) or seizures (clinical or electrical) thus meeting ONE of the following:

1      Normal background with some electrical seizure activity

2      Moderately abnormal activity (upper margin of trace >10µV and lower margin <5µV)

3      Suppressed activity (upper margin of trace <10µV and lower margin of trace <5µV)

4      Definite seizure activity

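### Neither the randomisation nor the stated analysis uses entry aEEG background, although it is the baseline state of time to normal aEEG, one of the three main markers

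*Protocol*

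**What the plan says.** **Analysis.** Section 9.1, repeated in the Protocol Summary, states "Data presentation will include descriptive statistics only". The summaries are to be compared between the two arms and with 45 recently treated cooled infants, and "Differences between the groups will be estimated". No covariate, stratum or adjusted estimate is named. The section also says "The study does of course not have the power to test outcome". It ranks feasibility of early recruitment first, and second whether the cooled-only arm gives marker values like those of the historical infants.

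**Allocation.** The Randomisation paragraph of section 3.1 and section 6.0 give 1:1 allocation by sealed opaque envelope. No stratification factor is named. "Sample size is 16 infants in each group".

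**Markers.** Section 2.1 lists three early predictors for the main analysis: time to recovery of a normal aEEG, MRI before 14 days, and peak LDH within 72 hours.

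**Entry aEEG.** Criterion C in sections 3.1 and 5.1 requires at least 30 minutes of aEEG from every infant. Its four items run from "Normal background with some electrical seizure activity" through moderately abnormal and suppressed background to definite seizures. Section 2.2 (Endpoint 12) also records aEEG background before xenon.

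**Use.** Section 2.0 (Primary Objective) hopes to see a trend in favour of xenon and intends the early predictors to supply the power calculation of a larger trial.

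**The concern.** Entry aEEG background is the starting point of the aEEG marker. An infant can enter with a background that is already normal; one with a suppressed trace starts furthest from the target. This follows from the protocol's own definitions.

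An unadjusted difference therefore carries two things: any effect of xenon, and whatever difference in starting severity the two groups happen to have. With 16 per arm that second part can be large enough to create or hide the trend that section 2.0 looks for, and the estimate then goes into the planning of a larger trial.

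The comparison of the cooled-only arm with the 45 historical infants is more exposed, because nothing in the design balances it. It also serves the second of the two purposes ranked in section 9.1.

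**Working it through.** **The plan's own figure.** "For pilot studies of this type the recommendation is a sample size of 12 per group", and the study was then enlarged "by increasing the number of babies by 8": 2 x 12 + 8 = 32, or 16 per arm. This reproduces. No alpha, power or effect size is given, so there is no power figure to check.

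**Inputs not in the protocol (assumptions).** The share p of infants with a suppressed entry trace, varied from 0.2 to 0.6; and the gap g between suppressed and other infants on the marker, in within-category SD, varied from 1 to 2.

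**1. How often the arms are unbalanced.** Each arm's suppressed count is taken as Binomial(16, p), independently.

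| p | gap of 3 or more infants | gap of 4 or more infants |
|---|---|---|
| 0.2 | 26% | 12% |
| 0.3 | 33% | 18% |
| 0.4 | 37% | 21% |
| 0.5 | 38% | 22% |
| 0.6 | 37% | 21% |

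With the suppressed total K fixed and the 32 infants split at random, the count in one arm is hypergeometric (32, K, 16). P(gap of 4 or more) is 25% (K = 10), 27% (12 or 20), 29% (14, 16 or 18), but 13.5% (11), 15% (13 or 19) and 16% (15 or 17). For an odd K the gap must be odd, so reaching 4 means reaching 5. The full range for K = 10 to 20 is 13.5-29%.

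**2. What a given imbalance does.** Shift = g x (difference in counts) / 16. For 10 v 6:
- g = 1: 1 x 4/16 = 0.25 SD
- g = 2: 2 x 4/16 = 0.50 SD

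**3. What adjustment gains.** Take p = 0.5 and within-category SD as the unit. The unadjusted SE is sqrt((1 + 0.25 g^2) x 2/16). The SE adjusted for one binary covariate is sqrt(2/16) x sqrt(1 + 1/28) = 0.360.

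| g | SE unadjusted | SE adjusted | change | equivalent per arm, 16 x (ratio of SEs)^2 |
|---|---|---|---|---|
| 0.5 | 0.364 | 0.360 | -1% | 16 |
| 1.0 | 0.395 | 0.360 | -9% | 19 |
| 1.5 | 0.442 | 0.360 | -19% | 24 |
| 2.0 | 0.500 | 0.360 | -28% | 31 |

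Simulation (20,000 trials each for g = 0.5, 1.0 and 1.5) gave unadjusted SEs of 0.363, 0.396 and 0.441, and adjusted SEs of 0.357, 0.360 and 0.360.

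In total-SD units the unadjusted 95% half-width is t(30) x sqrt(2/16) = 2.042 x 0.354 = 0.72 SD. Multiplying by sqrt(1 - R2) gives 0.63 SD if entry grade explains 25% of the variance and 0.52 SD if it explains 49%. Charging one degree of freedom for the covariate (2.045 in place of 2.042) leaves these unchanged to two decimals.

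**4. The historical comparison.** If the suppressed share differs by d between the cooled-only arm and the 45 infants, the unadjusted difference is off by g x d. For illustration, d = 0.20 (assumption) gives 0.2 SD at g = 1 and 0.4 SD at g = 2. This is systematic, so no interval around the unadjusted difference allows for it.

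**The case against.** **Section 9.1 is silent; it does not decide against adjustment.** A reader might infer that the protocol chose to disregard entry severity. The text does not say so: it names no estimator, and covariates are commonly left to an analysis plan, which is not at hand. That much stands. What remains is that 9.1 does fix the form of the analysis (descriptive, with differences), and that allocation, which only the protocol can settle here, names no stratum.

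**Chance imbalance is not bias.** A reader might infer that unstratified arms of 16 make the xenon comparison biased. They do not. Under 1:1 randomisation the imbalance averages to zero and the usual uncertainty of the unadjusted difference already includes it. The loss is in precision and in how the single realised estimate reads. This objection does not reach the historical comparison, which is not randomised. Section 9.1 describes the 45 infants as meeting the same entry criteria, but shared criteria still admit everything from a normal to a suppressed background.

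**The chance of imbalance is easily overstated.** A figure of 25-29% for a gap of four or more holds only for even suppressed totals; odd totals give about half that.

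**One marker of three.** The direct link to entry aEEG concerns time to normal aEEG. For MRI and peak LDH the protocol shows no such link.

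**The precision gain is assumed.** The documents give neither p nor g. The half-widths also suppose a complete, normally distributed value for all 16 infants, whereas section 3.1 puts mortality at about 25%, or 0.25 x 16 = 4 infants per arm, some of whom may die before the trace recovers. The figures show scale and do not forecast.

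**Criterion C is not a ready-made grade.** Its items overlap: a suppressed trace with seizures fits two of them. This stands, and the fix needs a collapsing rule.

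**Conclusion.** The concern holds in a limited form. The protocol makes no use, in allocation or in the stated analysis, of a baseline that eligibility obliges it to have and that is the starting state of one of its three main markers.

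For the randomised comparison the consequence is lost precision. A gap of four or more suppressed infants has a probability of about 12-22% (p from 0.2 to 0.6), or 13.5-29% for fixed totals of 10 to 20 among 32. A 10 v 6 split moves the estimate by 0.25-0.5 SD if g is 1-2. If g is only 0.5, adjustment gains almost nothing.

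For the historical comparison the consequence is possible confounding, and this is the stronger part of the point. The protocol does not show that the 45 infants differed in entry severity; it gives no way of allowing for it if they did.

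Nothing here affects the feasibility aim, and the study claims no power to test outcome. This is a worthwhile, low-cost improvement and does not correct an error that invalidates the plan.

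**What to change.** In section 9.1, beside each unadjusted between-arm difference for time to normal aEEG, report the difference adjusted for, or stratified by, entry aEEG background, with a 95% interval. Give the same for MRI and peak LDH as support.

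Fix the grade in advance as two levels, suppressed v not suppressed, read from the trace used for eligibility. Seizures are not a separate class; an infant who qualifies on seizures is graded by background.

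Do the same for the cooled-only arm against the 45 historical infants where their entry aEEG is on record, and state how many have one.

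The cost is one extra table column and one degree of freedom. To stay consistent with a descriptive plan, label the adjusted estimates as descriptive.
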